9.1 Subject Disposition

9.1.1 Subject Disposition

Patient disposition of the number of participants who consent, who are eligible and who are randomised as well as drop-out rates will be determined using information collected from the following CRF forms:

- Number assessed for eligibility: Inclusion criteria CRF (check all questions completed) / Exclusion criteria CRF (check all questions completed) & Confirmation of eligibility CRF (eligibility criteria confirmed)
- Number eligible /not eligible: Inclusion criteria CRF / Exclusion criteria CRF & Confirmation of eligibility CRF
- Number randomised: Randomisation CRF
- Number randomised to treatment arm who received treatment allocation:
 Randomisation CRF, IMP administration for all visits,
- Number for whom primary analysis data collected at 24 months:
 Ultrasonography CRF for 24 month visit
- Number withdrawn (including deaths) between Baseline and 24 months:
 Withdrawal CRF (withdrawal data / reason for withdrawal), End of study visit
 (end of study date /reason for termination / last study visit)

9.1.2 Consort Flow Diagram

9.2 Derived variables

Periportal Fibrosis is a binary outcome:

WHO ultrasonography Niamey protocol pattern scores of C, D, E or F=1 (i.e. has periportal fibrosis)

WHO ultrasonography Niamey protocol pattern scores of A or B=0 (i.e. does not have periportal fibrosis)

Kato-Katz egg counts

o Eggs Per Gram

The epg value for each participant visit is calculated in the macro database as the mean of the kato-katz slide egg counts from a maximum of 3 stool samples multiplied by an adjustment factor (one stool sample is sufficient for protocol adherence at a particular time point).

Helminth distributions within the human host are highly over dispersed therefore the epg values for each participant will be log transformed using natural logs (In).

A constant value of 1 will be added to all raw epg values to allow for the possibility of an epg value of 0.

$$\sum (\ln(epg+1))$$

The geometric mean epg will be calculated as below:

$$e^{\frac{\mathcal{E}(\ln(epg+1))}{n}} - 1$$

95% Cl's calculated on the logarithmic scale can also be converted back to the original scale by exponentiating and subtracting 1.

Egg Reduction Rate (ERR)

Sample Egg Reduction Rate will be estimated as:

$$(1-(epg2 \div epg1) \times 100)$$

Where epg1 and epg2 are the arithmetic mean of epg of faeces at:

- baseline and at 24 months + 4 weeks
- baseline and baseline + 4 weeks
- o 24 months and 24 months +4 weeks

o **Heavy Infection**

The WHO classifies 'Heavy infection' as those with epg counts of \geq 400. Where the percentage of children with of heavy infection is < 5% then morbidity control is considered to have been achieved and if the percentage of heavy infection is < 1% then the disease is considered to have been eliminated as a public health concern.

Heavy Infection: Binary variable $-1 = "yes" = epg \ge 400$, 0 = "no" = epg < 400 or not detectable

Disease status

Disease status is a binary variable where 0 = No disease (epg =0); 1 = Disease (>0 epg)

Point Prevalence (PP)

Is a measure of disease frequency and quantifies the proportion of individuals in a population who have Schistosomaisis mansoni at a specific instant in time.

$$PP = \frac{Total\ number\ of\ participants\ who\ have\ an\ average\ epg > 0}{Total\ number\ of\ participant\ at\ risk}$$

Total number of participants at risk will include all participants for whom at least one stool sample was collected at the timepoint being assessed.

Cure Rate (CR)

The CR is the proportion of participants who have changed from an epg >0 to and epg of =0 between timepoints;

 $CR = \frac{Total\ number\ of\ participants\ who\ have\ an\ average\ epg\ =\ 0\ at\ timepoint\ 1}{Number\ of\ participants\ who\ have\ epg\ >\ 0\ at\ timepoint\ 0}$

Residency in Holma district is dichotomised into 2 years - 4 years/ > 4 years

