5.2.2 Exploratory endpoints

- Schistosoma mansoni Egg Reduction Rate (ERR) measured between:
 - Point Baseline and baseline +4 weeks
 - Baseline and 2 years + 4 weeks
 - o 2 years and 2 years +4 weeks
- Prevalence at 2 years post 1st treatment.
- Cure rate between:
 - Baseline and baseline +4 weeks
 - o Baseline and 24 months
 - Baseline and 24 months +4 weeks
- Adverse Events measured at baseline and 24 months:
 - Any AE (Yes/No)
 - Digestive AE's = 4,5,6,7,or 12 on CRF see Also section 11 of SAP (Yes / No)
 - Neurological AE's 1,2,3,8,9 or III on CRF see Also section 11 of SAP (Yes/No)

[figure not shown]
6 Study Methods

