9.3 Protocol Deviations

All school-based trial activities were paused on 19th March 2020 in accordance with the Ugandan government announcement concerning COVID-19. Therefore, baseline data for the trial had been collected at different time-points.

Baseline data collected from Buhirigi was collected 17 months after MDA, in March 2020, Baseline data for Kaiso was collected 9 months after MDA, in March 2021.

In order to ensure data integrity a 10% resample of the Buhirigi baseline data was performed in March 2021 for the primary and secondary endpoints.

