9.6 Withdrawals

Listings of withdrawals from the trial (ordered by withdrawal reason) will be produced and will consist of the following variables:

- Subject ID
- Treatment group
- · Withdrawal reason
- School
- Gender
- Age

Time to withdrawal (days).

Summary statistics of the:

- withdrawal reason
- school
- gender
- age

will be produced according to section 9 using the safety population.

10 Efficacy Analysis

The primary and secondary efficacy analysis will be analysed using the full analysis population.

The following information will be summarised according to section 9 for the 24 months and 24 months +4 weeks follow up visits using the full analysis population. Box and whisker plots will be used to display continuous endpoints and stacked bar charts to represent binary and categorical endpoints.

- Niamey Protocol pattern score: (A /B /C / D / E //F)*
- Periportal fibrosis: (Yes / No) derived variable see section 9.2
- Infection intensity: EPG derived variable see section 9.2
- Infection intensity: Heavy infection derived variable see section 9.2
- Infection intensity ERR derived variable see section 9.2
- Infection: Point Prevalence derived variable see section 9.2
- Cure Rate derived variable see section 9.2

*Niamey Protocol pattern score will only be presented for the 24 month time point

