10.2.6 Analysis of secondary endpoint - Cure rate

The cure rate as defined in section 9.2 will be calculated for the following time points:

- Baseline to 24 months
- Baseline to baseline +4 weeks
- 24 months to 24 months + 4 weeks

Cure rates will be presented by treatment arm and also stratified by baseline infection intensity; \geq 400 epg = Heavy infection / <400 - 1 epg = Medium - Light Infection.

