15.1.1 Protocol v 2.0

- Updated CI Maternity Cover (Front page, Section 2 Trial Management Committees and Section 26.3 Safety Reporting Flow Chart)
- Addition of 'school-community based' to aim (Section 7) to enable trial activities to be carried out whilst schools are closed due to COVID-19 National Guidelines
- Addition Section 9 Community School and Trial Team COVID-19 precautions.
- Section 11.1.1.2 removal of IMP expiry date of 31/01/2022, as trial will run beyond this date due to COVID-19 pause of trial activities.
- Addition of 'local community trial site location' and 'house-hold to house-hold' throughout the protocol to enable trial activities to be carried out in the appropriate locations whilst the schools are not permitted to be used for trial activities due to COVID-19 restrictions. (Section 12)
- Explicit statement that trial activities to return to the participating school location when allowed. (Section 12)
- Clarification of exploratory outcome sample collection (Section 12.3.3).
- Addition of participant photograph to enhance participant identification for community based trial activities (Section 12.3.3.1)
- Widening of window between baseline assessments and IMP administration so that baseline data may be used. Delay between activities caused by COVID-19 pause to trial activities. (Section 12.4)
- Addition Section 12.4.1 Baseline Assessment Assurance following COVID-19 Pause. Text added to allow repeat collection of primary and secondary endpoint data from Buhirigi School participants to verify data integrity despite time delay between first collections and IMP administration caused by COVID-19 pause.
- Section 12.5.3 Addition of footnotes to the Schedule of assessments to allow for wider window between ultrasound examination and first IMP administration at baseline visit, due to COVID-19 pause.
- Widening of temperature storage range for collected samples (Section 16)

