16.1.2 Change to definition of Full Analysis population

Removal of the condition to only include participants 'treated at baseline' in the population. Due to the COVID 19 pandemic many participants were not treated at baseline but were treated at other time points in the trial. Including only participants treated at baseline would significantly reduce the sample size and reduce the power. Also information would be lost for those participants not treated at baseline but treated at other time points

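### The cure-rate formula contradicts its own definition, and the baseline four-week ERR and cure rate take in undosed children and, in Buhirigi, stools from before the COVID delay

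*SAP*

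**What the plan says.** - **Cure rate, words (9.2).** "The CR is the proportion of participants who have changed from an epg >0 to and epg of =0 between timepoints".
- **Cure rate, formula (9.2).** The numerator is the total with an average epg of 0 at timepoint 1. The denominator is the number with epg > 0 at timepoint 0. Neither term requires a stool at both visits or a dose in between. Section 10.2.6 takes its definition from 9.2.
- **Population (10).** "The primary and secondary efficacy analysis will be analysed using the full analysis population". ERR and cure rate sit under 10.2. Section 8.2.1 puts no treatment condition on this population. Section 16.1.2 explains that being treated at baseline was dropped as a condition because "many participants were not treated at baseline but were treated at other time points in the trial".
- **Timing (9.3, 15.1.1).** "Baseline data collected from Buhirigi was collected 17 months after MDA, in March 2020"; Kaiso followed in March 2021. Activities paused on 19 March 2020. The window between baseline assessment and dosing was widened so that the March 2020 data could stand, and a resample was added "to verify data integrity despite time delay between first collections and IMP administration caused by COVID-19 pause". Section 9.3.1 says resampled children cannot be linked to their 2020 records.
- **Third cure-rate interval.** Section 5.2.2 has "Baseline and 24 months +4 weeks"; section 10.2.6 has "24 months to 24 months + 4 weeks".

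**The concern.** The sentence and the formula in 9.2 give different numbers unless every child is positive at timepoint 0, or no child negative at timepoint 0 is negative again at timepoint 1 (with every positive child giving a second stool). A programmer following the formula could report a proportion above 100%.

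The interval from baseline to baseline + 4 weeks raises a different problem. All three arms are scheduled one dose at baseline (9.5), so this interval holds no contrast between regimens. Its main use is to describe response to a dose. Including children who had no dose dilutes that response. Starting from a stool taken long before the dose mixes in whatever happened to egg counts during the wait. The baseline ROC curves and adverse-event regressions in 11.1.3 relate baseline epg to adverse events at first dosing, so in Buhirigi they share the timing problem.

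**Working it through.** The SAP states no cure rate or ERR, so there is no figure to reproduce. It also gives no infection prevalence, cure probability, undosed share or change in egg counts before dosing. Every input below is an assumption, shown over a range.

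**1. Cure-rate formula.** Let p = share with epg > 0 at timepoint 0, c = true cure among them, s = share of timepoint-0 negatives still negative at timepoint 1. With complete stools:

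- Paired definition: CR = c.
- Printed formula: CR = [p·c + (1 − p)·s] / p = c + s(1 − p)/p.

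Single cases with c = 60%, s = 95%:
- p = 0.70: (0.42 + 0.285)/0.70 = 1.007, or 101%.
- p = 0.50: (0.30 + 0.475)/0.50 = 1.55, or 155%.

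Range with c = 50–70%, s = 80–95%:

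| p | Printed formula | Paired |
|---|---|---|
| 0.9 | 59–81% | 50–70% |
| 0.8 | 70–94% | 50–70% |
| 0.6 | 103–133% | 50–70% |
| 0.4 | 170–213% | 50–70% |

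The result passes 100% when p < s/(1 + s − c). That is p below 0.8/1.3 = 0.62 at the low end of these ranges and below 0.95/1.25 = 0.76 at the high end.

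**2. Missing second stool.** If a share m of infected children give no stool at timepoint 1, they stay in the denominator and cannot enter the numerator, so their contribution is (1 − m)·c. With c = 60%, m = 10% gives 54%. With m = 25% (the loss allowance in section 7, borrowed only as an illustration) it gives 45%. This error runs opposite to the one in step 1, so the two can partly mask each other.

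**3. Undosed children, baseline to baseline + 4 weeks.** Let u = undosed share, f = share of undosed positives reading epg 0, E = true ERR. Assume undosed children gave the second stool, had similar starting means and unchanged mean counts.

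- CR = (1 − u)·c + u·f. With c = 70%, f = 10%: u = 10% gives 64%, u = 20% gives 58%, u = 50% gives 40%.
- ERR = (1 − u)·E. With E = 90%: u = 10% gives 81%, u = 20% gives 72%, u = 50% gives 45%.

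**4. Old Buhirigi stool.** Let k = mean epg at dosing divided by mean epg in March 2020. Apparent ERR = 1 − k(1 − E). With E = 90%: k = 0.5 gives 95%, k = 1 gives 90%, k = 2 gives 80%, k = 3 gives 70%. The bias can go either way and is nil if counts did not change.

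Length of the delay: if the March 2021 resample preceded first dosing, the gap is at least 12 months, and the nominal four-week interval spans about 13. The SAP gives no first-dose date.

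**5. Intervals.** Sections 5.2.2 and 10.2.6 agree on baseline to baseline + 4 weeks and baseline to 24 months. They differ on the third: one starts at baseline, the other at 24 months.

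**The case against.** **The sentence is right, and 10.2.6 supports it.** Cure rates are also to be split by baseline intensity into heavy infection and a lower stratum starting at 1 epg. A child with epg 0 at baseline belongs to neither. This stands as evidence of intent, so it would be too strong to infer that the wrong children will certainly be counted. It does not remove the contradiction, because 10.2.6 sends the reader back to 9.2 for the definition.

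**The delay and missed doses are acknowledged.** Section 9.3.2 compares the 2020 and 2021 egg counts by a distribution plot, a Kolmogorov-Smirnov test and a linear model, and 9.5 tabulates missed doses. That is useful context. But 9.3.2 states no consequence if the distributions differ, and 9.5 does not alter who enters ERR or cure rate.

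**Transmission is intense, so prevalence may be high.** At p = 0.9 the printed formula stays below 100%. This is fair: the size depends on figures the SAP does not give.

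A reader might go on to infer several stronger things that the document does not support:

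- *That ERR and cure rate cannot measure drug response at all.* The interval from 24 months to 24 months + 4 weeks does not use the old stool, and every arm has a dose scheduled at 24 months. Kaiso's baseline is not affected by the March 2020 timing either. The numerator error concerns cure rate only.
- *That a one-year gap is established.* It is an inference from the resample date.
- *That a community treatment round fell inside Buhirigi's gap.* Kaiso's baseline was 9 months after a round, which implies about June 2020, but the SAP does not say that round reached Buhirigi.
- *That the resample mean could replace the old baseline.* ERR is estimated by arm, the 10.2.4 model needs individual baseline counts, and cure rate needs pairs. An unlinked 10% resample supplies none of these.

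**Conclusion.** The cure-rate formula is wrong as printed and contradicts the sentence above it. Negatives at both visits push the rate up, by about 9 to 11 points at 90% prevalence and past 100% below roughly 62–76% prevalence, under the assumed cure and persistence rates. Missing second stools pull it down.

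The two problems with the baseline four-week summaries also hold, within limits. The population includes children not treated at baseline, described as many but not counted. The old stool concerns Buhirigi only, and only results anchored at baseline; its direction and size are unknown. The mismatch in the third cure-rate interval is plain on the text.

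Section 5.2.2 lists ERR and cure rate as exploratory, although the headings in 10.2 call them secondary. Cure rate is descriptive, with no model or test. The primary endpoint and its gatekeeping sequence are untouched. The correction is worth making because it is cheap and because a cure rate above 100% would be indefensible in a report.

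**What to change.** 1. **Formula (9.2).** Define cure rate as children with epg > 0 at timepoint 0 and epg = 0 at timepoint 1, divided by children with epg > 0 at timepoint 0, both limited to children with a stool at both visits.
2. **Four-week drug-response summaries.** For ERR and cure rate over baseline to + 4 weeks and 24 months to + 4 weeks, restrict to children dosed at the start of the interval with stools at both visits, and state the number excluded.
3. **By school.** Report baseline-anchored ERR, cure rate and the baseline ROC and adverse-event analyses by school, with Buhirigi flagged for the delay and its first-dose dates given. There is no need to discard Buhirigi.
4. **Intervals.** Reconcile the third cure-rate interval between 5.2.2 and 10.2.6, or list both.

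The cost is SAP wording and data filters. The downside is fewer children in the four-week summaries. At 24 months the dosed subset is also selected on adherence after randomisation, so it describes drug response and should not be presented as a randomised comparison between arms.

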9.3 Protocol Deviations

All school-based trial activities were paused on 19th March 2020 in accordance with the Ugandan government announcement concerning COVID-19. Therefore, baseline data for the trial had been collected at different time-points.

Baseline data collected from Buhirigi was collected 17 months after MDA, in March 2020, Baseline data for Kaiso was collected 9 months after MDA, in March 2021.

In order to ensure data integrity a 10% resample of the Buhirigi baseline data was performed in March 2021 for the primary and secondary endpoints.

9.3.1 Baseline data Unpaired Analysis

Data for participants who had baseline data re-sampled in March 2021 could not be linked to their baseline data taken in March 2020 since ID data required to match the participants was not recorded / not available. Therefore an unpaired analysis as detailed below will be performed since the matched analysis detailed in the Final SAP V1.0 section 9.3 is not possible due to lack of linkage information.

9.3.2 Schistosoma mansoni infection intensity by faecal egg count

An Empirical cumulative distribution plot of In(epg+1) of all 2020 and the 2021 resample will be produced. The Kolmogorov-Smirnov test will be performed to determine if the two distributions are equivalent.

An unpaired analysis of all the baseline data from 2020 and the resampled 2021 data will be performed using the following linear model, where 'Cohort' is the year of baseline data:

Im (Y ~ Cohort)

9.3.3 WHO ultrasonography score

An unpaired analysis of all the baseline data from 2020 and the resampled 2021 data will be performed using the following generalised linear model, where 'Cohort' is the year of baseline data:

 $glm (Y \sim Cohort, family = binomial)$

A post hoc decision was taken to not conduct this analysis due to all ultrasound scores being identical in the resampled data and a very small proportion of participants had fibrosis in the 2020 data.

9.4 Demographic and Baseline Variables

The following demographic and baseline variables will be captured in the Demographic CRF, Ultrasonography CRF, Stool sample (1,2 & 3) CRF's & Ultrsonography adjudication CRF and will be summarised according to section 9 using the Full Analysis population.

9.4.1 Demographics

- Age at enrolment: (years)
- Sex: (male/female)
- School: (Buhirigi / Kaiso)
- Class: (class 1, class 2, class 3, class 4)
- Residency in Hoima district: (2 years 4 years)

9.4.2 WHO Ultrasonography score

- Niamey Protocol pattern score; (A /B /C / D / E /F)
- Periportal fibrosis: (Yes / No) derived variable see section 9.2.

9.4.3 Schistosoma Infection Intensity / infection

Eggs per gram (EPG): - Derived variable see section 9.2

Heavy infection intensity: (Yes / No) - derived variable see section 9.2

Egg Reduction Rate (ERR): - Derived variable see section 9.2

Cure Rate (CR):-Derived variable see section 9.2

Point Prevalence (PP): - Derived variable see section 9.2

9.5 Treatment Compliance

Information relating to the number of participants who missed the IMP at the required visit captured in the 'Non-Adherence to protocol' CRF as well as the 'IMP administration' CRF will be shown in a summary table and displayed as a stacked bar chart, each treatment group represented by their colour and position within the stack. The number missing will be a scale on the y axis and each treatment time—point will be ordered on the x axis.

- · Standard of Care Arm: Baseline, 12 months and 24 months
- Intervention Arm 1 (2 x treatment): Baseline, month 7, month 12, month 19 and month 24
- Intervention arm 2 (4 x treatment): Baseline, month 4, month 7, month 10, month 12, month 16, month 19, month 22 and month 24

Information relating to the number of participants who missed data collection visits captured in the 'Non-Adherence to protocol' CRF will be shown in a summary table and displayed using a stacked bar chart with each treatment arm represented by their colour and position within the stack, the number missing will be shown on the y axis and time-point on the x axis.

- Ultrasonography
- Parasitology
 - Standard of Care Arm: Baseline and 24 months
 - o Intervention Arm 1: Baseline and 24 months
 - o Intervention arm 2: Baseline and 24 months

9.6 Withdrawals

Listings of withdrawals from the trial (ordered by withdrawal reason) will be produced and will consist of the following variables:

- Subject ID
- Treatment group
- · Withdrawal reason
- School
- Gender
- Age

Time to withdrawal (days).

Summary statistics of the:

- withdrawal reason
- school
- gender
- age

will be produced according to section 9 using the safety population.

10 Efficacy Analysis

The primary and secondary efficacy analysis will be analysed using the full analysis population.

The following information will be summarised according to section 9 for the 24 months and 24 months +4 weeks follow up visits using the full analysis population. Box and whisker plots will be used to display continuous endpoints and stacked bar charts to represent binary and categorical endpoints.

- Niamey Protocol pattern score: (A /B /C / D / E //F)*
- Periportal fibrosis: (Yes / No) derived variable see section 9.2
- Infection intensity: EPG derived variable see section 9.2
- Infection intensity: Heavy infection derived variable see section 9.2
- Infection intensity ERR derived variable see section 9.2
- Infection: Point Prevalence derived variable see section 9.2
- Cure Rate derived variable see section 9.2

*Niamey Protocol pattern score will only be presented for the 24 month time point

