8.2.1 Full Analysis Population

- All participants who were consented, eligible and randomised
- Any participant who had an ultrasound score of X,Y or Z at baseline will be withdrawn from the trial and is therefore not included in the 'Full Analysis Population'
- Any participants whose re-consent was required but not obtained are withdrawn from the trial and are not therefore included in the 'Full Analysis Population'

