8.2.2 Safety Population

 All subjects who were consented and randomised and received any dose of the IMP irrespective of whether or not they were eligible.

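### The withdrawal summary in SAP 9.6 uses the safety population, so children who leave before any dose drop out of it, most of all in the control arm

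*SAP*

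**What the plan says.** Section 9.6 plans two outputs on withdrawals. The first is a listing with subject ID, treatment group, reason, school, gender, age and time to withdrawal; no analysis population is named for it. The second is a set of summary statistics for reason, school, gender and age, which "will be produced according to section 9 using the safety population".

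Section 8.2.2 defines the safety population as "All subjects who were consented and randomised and received any dose of the IMP irrespective of whether or not they were eligible". Membership therefore needs at least one dose.

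Section 16.1.2 explains why the full analysis population no longer requires treatment at baseline: "many participants were not treated at baseline but were treated at other time points in the trial".

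Section 9.5 gives the dosing visits:
- control: "Standard of Care Arm: Baseline, 12 months and 24 months"
- 2x arm: "Intervention Arm 1 (2 x treatment): Baseline, month 7, month 12, month 19 and month 24"
- 4x arm: "Intervention arm 2 (4 x treatment): Baseline, month 4, month 7, month 10", and further visits to month 24.

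Section 9.1.1 takes the number withdrawn between baseline and 24 months from the withdrawal and end-of-study forms, again without a dose condition.

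**The concern.** A summary of withdrawals should describe everyone who could have withdrawn, which means everyone randomised. Making entry depend on a dose removes the children who left earliest. In this trial the removal is also uneven across arms, because a child undosed at baseline gets a second chance of entering the safety population at different times: soonest in the 4x arm and latest in the control arm. A control child who missed the baseline dose and left before month 12 cannot enter the table, while a similar child in the 4x arm may already have been dosed at month 4.

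The group is plausible here. Under section 6.3, children receive a pre-randomised identification number on enrolment. Section 9.3 records that school-based activities paused in March 2020, the month in which baseline data were collected at one school. Section 7 says that some enrolled children could not be located after the restart.

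At stake is the by-arm reading of this table. With equal true withdrawal, it would show fewer withdrawals in the control arm than in the 4x arm. It also might not agree with the CONSORT count.

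**Working it through.** The SAP states no number of withdrawals by arm and no number of undosed children, so there is no figure of its own to reproduce. The direction follows from the text. The size can only be illustrated.

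**Direction.** For a child undosed at baseline, the first scheduled dose after that (section 9.5) is at month t = 12 (control), 7 (2x) or 4 (4x). Any withdrawal before t is outside the safety population. The longer the gap, the more withdrawals are omitted.

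**Inputs**
- 200 per arm: 600 in total (section 7), allocated 1:1:1 (section 6.1).
- Withdrawal by 24 months, W: 25%, taking the loss to follow-up planned in section 7 as the withdrawal rate. W = 50% is also tried, because section 8.4 works with 300 outcomes, half of 600.
- Fraction undosed at baseline, m: not given. Assumed equal across arms; 10%, 20% and 40% are tried.
- Assumed: constant withdrawal hazard, and the next scheduled dose is taken if the child is still in the trial.

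**Formulas**
- Probability of withdrawing before month t: P(t) = 1 − (1 − W)^(t/24)
- Withdrawals omitted per arm: 200 × m × P(t)
- Share of the arm's withdrawals omitted: m × P(t) / W

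**W = 25%** (50 true withdrawals per arm)
- Control: P(12) = 1 − 0.75^(12/24) = 0.134
- 2x: P(7) = 1 − 0.75^(7/24) = 0.080
- 4x: P(4) = 1 − 0.75^(4/24) = 0.047

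| W | m | Omitted, 1x | Omitted, 2x | Omitted, 4x |
|---|---|---|---|---|
| 25% | 0 | 0 | 0 | 0 |
| 25% | 10% | 2.7 (5.4%) | 1.6 (3.2%) | 0.9 (1.9%) |
| 25% | 40% | 10.7 (21.4%) | 6.4 (12.9%) | 3.7 (7.5%) |
| 50% | 20% | 11.7 (11.7%) | 7.3 (7.3%) | 4.4 (4.4%) |

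Cells give children omitted per 200 randomised, with the share of that arm's withdrawals in brackets.

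**What the table would show.** With W = 25% and equal true withdrawal, the 4x-to-control ratio of displayed withdrawals is (50 − 0.9)/(50 − 2.7) = 49.1/47.3 = 1.04 at m = 10%, and (50 − 3.7)/(50 − 10.7) = 46.3/39.3 = 1.18 at m = 40%. The true ratio is 1.

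**Sensitivity.** If only 70% attend each later dose, the omissions rise but keep their order (W = 25%, m = 10%: 3.4, 2.1 and 1.2). Over m from 5% to 40%, W from 25% to 50% and attendance of 70% or 100%, the control arm loses about 2.5 to 2.9 times the share that the 4x arm loses.

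**The case against.** The strongest reply is that nothing is lost from the report as a whole. The 9.6 listing carries treatment group, reason, school, gender, age and timing with no dose condition, and the 9.1.1 count includes every withdrawal. Section 9 also requires each table to show its population size by arm, so a reader could see the shortfall. This stands, and it confines the problem to one table. It does not remove it: a line listing is not a by-arm summary, and a table that cannot be reconciled with the flow diagram needs explaining.

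A second reply is that section 16.1.2 refers to children who missed baseline but were dosed later, and those children are in the safety population. That is correct. Only children who left before any dose are affected, and the SAP does not say how many there were.

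Two stronger readings are tempting and are not supported.
- A reader might infer that this table is the evidence on which the missing-at-random assumption and the complete-case analysis rest. The SAP does not say so. Section 8.4 plans a graph of missing data and a sensitivity analysis, and section 9.5 plans a table and chart of missed data-collection visits by arm.
- A reader might infer a large false excess in the 4x arm. Placing every withdrawal at month 8, with each dose missed independently with probability 0.3, leaves 40 × (1 − 0.3) = 28 control and 40 × (1 − 0.3³) = 38.9 4x withdrawals displayed out of 40 each, a 39% excess. Both choices are unsourced. With the same 0.3 but a constant hazard and 25% withdrawal, about 20% and 7% are omitted, and the excess is 0.927/0.797, about 16%.

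**Conclusion.** The point holds as a minor reporting flaw. As written, sections 9.6 and 8.2.2 together leave out withdrawals before first dose, and the section 9.5 schedule makes this most frequent in the control arm if similar fractions are undosed at baseline in each arm. The direction rests on the SAP's text and that assumption. The size does not come from the SAP: it runs from nothing, if all were dosed at baseline, to about a fifth of control-arm withdrawals under 25% withdrawal with 40% undosed at baseline and later doses taken. No efficacy estimate, test or confidence interval changes.

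**What to change.** In section 9.6, base the summary on all randomised participants, by arm, as far as consent allows, in place of the safety population. Show withdrawals before and after first dose separately. Give separate rows for children not re-consented (a count only, where consent does not allow more) and for those removed for a baseline X, Y or Z score. Reconcile the totals with the CONSORT counts. Keep the safety population for the section 11 analyses.

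The full analysis population would not be an adequate substitute, because section 8.2.1 excludes children with X, Y or Z at baseline and also those not re-consented: "Any participants whose re-consent was required but not obtained are withdrawn from the trial".

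The cost is a short change of wording and one table rerun. The withdrawal and end-of-study data come from forms already named in section 9.1.1, which also names the form recording IMP administration.
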